will use our secure VA Research Server under the direction of [name] as the Study Data Core. All study related committees will meet at the offices of the VA Outcomes Group, either in person or using existing secure teleconference facilities. Web-based study team meetings will be held every other week, and will use videoconference to minimize expense. Two study meetings will be held at the annual meetings of the Association of VA Surgeons and at the Society for Vascular Surgery during each year of the study. This will serve as a cost-effective way for our group to meet biannually during the study period.

Characteristics and selection of the study population: Our study population will be Veterans and vascular surgeons enrolled at the ten intervention sites and ten control sites in our cluster-randomized trial. The inclusion criteria for patients will be Veterans with a >5.0 cm AAA that are candidates for endovascular and open repair. Step C of the Study Procedures describe the recruitment procedures and inclusion criteria in detail.

STUDY PROCEDURES

Step A: Recruitment of Surgeons Twenty VA hospitals that currently perform both endovascular and open repair are the study sample. Each local site investigator has been interviewed and their credentials vetted by the PI, and has accepted to participate in the study. Local site investigators may invite one or two additional surgeons whom they work with at their site to participate in the study. Site Study Coordinators will provide surgeons the Study Invitation and Information Sheet at the start of the study period and document the date. A waiver of documentation of informed consent for surgeons will be requested since the surgeon's participation involves no procedures other than completion of a survey and presents no more than minimal risk.

Step B: Selection of Intervention Centers: In Aim 1, we will conduct the intervention in 120 patients across 10 VA hospitals randomly assigned to the intervention arm. We will have a 9:1 stratified randomization scheme, so that we have a similar proportion of Complex and Intermediate Surgical VA hospitals in the intervention and control arms. These are the only two types of VA hospitals that perform AAA repair. Sites will be randomized at IRB approval in a rolling fashion. Site specific Study Coordinators will use the Study Protocol to facilitate IRB approval.^{3, 15}.

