The patient will be remunerated at completion of the enrollment visit. Data will be recorded securely by the Site Study Coordinator.

The Veteran will be thanked for their participation by the study team via a formal letter mailed from the Principal Investigator.

Process at the Control Sites:

Step 1: The Study Coordinator will administer the Survey. (10 minutes)

Step 2: The Study Coordinator will escort the patient to the visit with the vascular surgeon.

Step 3: After the Visit, the Site-Specific Research Coordinator will complete the Decision-Process Score with the Veteran. (5 minutes)

Step 4: Thirty days after AAA repair, the Study Coordinator will complete the PSQ-18 with the

Veteran. (5 minutes)

The patient will be remunerated at completion of the enrollment visit. Data will be recorded securely by the Site Study Coordinator.

The Veteran will be thanked for their participation by the study team via a formal letter mailed from the Principal Investigator.

Surgeon survey administration at both the intervention and control sites:

Step 1: The Study Coordinator will administer the Pre-Visit Survey to the surgeon (1 minute, according to pilot testing at four sites in the trial, and two sites outside the trial).

Step 2: The surgeon will have the clinic visit with the Veteran.

[figure not shown]
Step 3: After the Visit, the Study Coordinator will complete the Post-Visit Survey with the surgeon (1 minute).

Data will be recorded securely by the Study Coordinator.

Recruitment Target: We will recruit 12 Veterans per site (4 Veterans per site per month for 3 months) at 10 sites in the intervention arm for a total of 120 Veterans in the intervention arm. We will recruit 12 Veterans per site (4 Veterans per site per month for 3 months) at 10 sites in the control arm for a total of 120 Veterans in the control arm. The unit of analysis will be the Veteran. Randomization will occur at the site level, in a stratified 9:1 randomization scheme, based on the VA hospital's Surgical Complexity designation. We will enroll 8 Complex and 2 Intermediate sites per arm. Randomization will occur at the time of IRB approval. Weekly conference calls with Site Study Coordinators will assess study enrollment rates and help with problem-solving.

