Aim 1. Dependent and Independent Variables: The main dependent variable in Aim 1 is the preference for repair type (endovascular or open) as expressed by Veterans and surgeons in their respective survey instruments. Each survey instrument has a validated coding algorithm which will be used to categorize survey responses into preference for endovascular or open repair (Appendix 2)⁴⁴. Independent variables, such as age, gender, race, ethnicity, and other descriptive variables are recorded as part of the survey instrument by the Site Study Coordinator. Hospital and surgeon characteristics such as annual hospital and surgeon volume of endovascular and open repair for each participating site will be collected via VINCI by [name]. These variables will be measured at the hospital level, as in prior analyses.^{65, 97-100}

Aim 1: Data analytic strategy: tests, strengths, limitations, and alternative approaches: In Aim 1, our main outcome variable will be Veteran and surgeon preference for repair type (endovascular or open repair). The preference will be defined as either preference for endovascular or preference for open repair. Repair type preference will be categorized from several questions in our survey instruments. Several questions allow for differing degrees of choice (e.g., strongly/slightly favor open repair). For these responses, we will use variables that allow this category. We will use a coding algorithm (Appendix 2) which deconstructs survey questions into components that generate binary outcomes (i.e., preference for open or endovascular repair) and allows sensitivity analyses using the gradients. We will compare the proportion choosing each repair type in the intervention and control groups to test the effect of the decision aid on repair type preference. The proportions preferring each repair type will be compared between the two groups accounting for clustering of patients within center and/or surgeon; in particular, we will use the Mantel-Haenszel test (for stratified contingency tables, equivalent to partial likelihood ratio test from fixed effects logistic regression) or a mixed effects logistic regression with fixed effect of group, and random intercept for center effects.

Aim 1 Data Collection Strategy: potential problems and solutions Refer to Section 6 of this Protocol Coding Guide and Data Management Plan.

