10	10	12	12	120	120	0.9	0.25	0.68	0.96	0.86
10	10	12	12	120	120	0.9	0.20	0.73	0.88	0.75
10	10	12	12	120	120	0.9	0.15	0.78	0.71	0.50

We adjusted our sample size calculations for our cluster-randomized trial to account for intra-cluster correlation, and allow for variable enrollment size within each cluster. As shown in Table 8, we anticipate that we will have 96% likelihood of detecting a 25% effect size, assuming an ICC of 0.01. Sensitivity analyses around our ICC assumption of 0.01 demonstrate that even if our ICC is ten times higher (ICC=0.10), our sample size would still yield an 81% likelihood of detecting a 25% effect size between intervention/control.

Aim 2: To determine the effect of the decision aid on agreement between preferences and repair type.

Aim 2 Dependent and Independent Variables: After identifying Veterans' preference for endovascular or open repair, we will determine the agreement between their preferences and the repair types they receive. The dependent variable will be the kappa statistic (κ), measuring agreement between the preferred repair type and the repair type the Veteran ultimately receives. Cohen's kappa will be compared between the intervention and control groups. Kappa will be calculated overall and by hospital (using a weighted sum of the kappas for each hospital in that arm). As a secondary outcome, Site Study Coordinators will administer two surveys to the Veteran. These two surveys will examine patient satisfaction (PDQ-18) and shared decision making (Decision Process Score, or DPS)^{87, 104}. Our group has used these or similar instruments in prior work^{104, 105}. A survey administration training guide for each Site Study Coordinator has been developed. The DPS will be administered at the end of the visit, and the PDQ-18 will be completed at 30-day follow-up visits which are already standard practice after AAA repair for both repair types. Completing the surveys in this context will not require any extra visits by Veterans, an important strength given the elderly population of patients involved in our proposal.

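### For Aim 1, the Mantel-Haenszel/fixed-effects option cannot serve a site-randomised comparison: on centre strata it has no value, and on complexity strata it ignores site clustering

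*Combined protocol and SAP*

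**What the plan says.** Section 7, under the Aim 1 data analytic strategy, says the proportions preferring each repair type will be compared between arms "accounting for clustering of patients within center and/or surgeon". It then gives two ways to do so. The first is "we will use the Mantel-Haenszel test (for stratified contingency tables, equivalent to partial likelihood ratio test from fixed effects logistic regression"; the second is "or a mixed effects logistic regression with fixed effect of group, and random intercept for center effects". It does not say what the Mantel-Haenszel strata are, nor when one option is to be used rather than the other.

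The unit of allocation is set in Section 4. Step B speaks of "10 VA hospitals randomly assigned to the intervention arm". The Recruitment Target paragraph says "Randomization will occur at the site level, in a stratified 9:1 randomization scheme, based on the VA hospital's Surgical Complexity designation" and adds "We will enroll 8 Complex and 2 Intermediate sites per arm", with 12 Veterans recruited at each of 20 sites. The Aim 1 power analysis is adjusted for intra-cluster correlation, with a base ICC of 0.01 and further columns in Table 3 for 0.05 and 0.10.

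**The concern.** A Mantel-Haenszel test, or a logistic model with a fixed effect for each stratum, draws its information on the arm effect from contrasts within strata. When whole sites are randomised there is no such contrast within a centre, nor within a surgeon who works at one study site. The first option therefore looked unusable on the strata the sentence points to. The only other stratum in the documents, surgical complexity, does contain both arms, but using it would not account for site clustering, which is the purpose the sentence states.

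The stake differs by reading. With centre strata the test gives no result, and the failure would be noticed. With complexity strata the software returns an ordinary-looking p-value that is too small if sites differ. Because the options are joined by 'or', the analyst could then choose between two results that need not agree.

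**Working it through.** **Inputs from the documents.** 20 sites, 10 per arm (8 Complex and 2 Intermediate), 12 Veterans per site, 120 per arm; 90% preferring endovascular repair in control, 68% in intervention (Table 3); ICC 0.01, 0.05 and 0.10.

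**Assumptions not in the documents.** Two-sided 5% level for Aim 1 (only the Aim 2 calculation states a two-tailed test); exactly 12 per site; the same 90% preference in both complexity strata; beta-distributed site rates.

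**1. The plan's own power figures.** The text gives 96% at ICC 0.01 and 81% at ICC 0.10 for the 25% effect. Design effect DE = 1 + 11 × ICC, so 1.11 and 2.10. Effective n per arm = 120/DE = 108.1 and 57.1. Standard error = √[(0.90×0.10 + 0.68×0.32)/n] = √(0.3076/n) = 0.0533 and 0.0734. Difference/SE = 0.22/SE = 4.12 and 3.00. With a t reference on 18 df the power is 97.4% and 80.9%, within two points of the stated figures. The sample size therefore presumes a test whose variance allows for clustering.

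**2. Centre as the stratum.** In each stratum the Mantel-Haenszel variance is n₁n₀m₁m₀ / [N²(N−1)], where n₁ and n₀ are the numbers in the two arms and m₁ and m₀ the numbers preferring each repair. At every site n₁ or n₀ is 0, so each variance term is 0. Observed equals expected at every site, so the numerator is 0 as well. The statistic is 0/0, and so is the Mantel-Haenszel odds ratio. In the fixed-effects model, 20 centre effects plus arm make 21 columns of rank 20, so the arm coefficient is not identified. None of this depends on the ICC, the site size or the preference rate. The '9:1' wording does not alter it, since any site-level allocation leaves each centre in one arm.

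**3. Complexity as the stratum.** The strata hold 8×12 = 96 v 96 and 2×12 = 24 v 24 Veterans. The test is computable but uses the binomial variance, which is too small by the factor DE. Approximate type I error = 2[1 − Φ(1.96/√DE)]. The simulated columns come from 40,000 null beta-binomial trials per ICC.

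| ICC | DE | 1.96/√DE | Formula | Simulated | Simulated, continuity-corrected |
|---|---|---|---|---|---|
| 0.01 | 1.11 | 1.860 | 6.3% | 6.3% | 3.7% |
| 0.05 | 1.55 | 1.574 | 11.5% | 11.8% | 8.0% |
| 0.10 | 2.10 | 1.353 | 17.6% | 18.1% | 13.3% |

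On the same data, a site-level regression of proportions on arm and complexity, referred to t(17), gives 4.8%, 4.9% and 4.6%.

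**4. The option that works.** The listed mixed model (arm plus random centre intercept) was fitted by maximum likelihood with 25-point quadrature to 4,500 null trials per ICC; the Monte Carlo standard error is about 0.3 to 0.4 points.

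| ICC | Wald z | t(18) | Complexity added, z | Complexity added, t(17) |
|---|---|---|---|---|
| 0.01 | 4.2% | 3.4% | 4.4% | 3.4% |
| 0.05 | 5.9% | 4.2% | 6.4% | 4.6% |
| 0.10 | 7.3% | 5.3% | 7.8% | 6.0% |

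**The case against.** The strongest reply is that the plan already holds the answer. The same sentence lists a valid mixed model, under a heading that announces alternative approaches. With centre strata nobody can be misled, because the test produces no output. The inflated error rates belong to complexity strata, which the sentence never mentions. Even there, at the planning ICC, the error is 6.3%, or 3.7% with continuity correction. The documents give no evidence that the true ICC is 0.05 or 0.10.

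Much of this stands. Aim 1 remains analysable, the error rates are conditional on a reading the plan does not state, and they are small at ICC 0.01. It does not rescue the clause, however. On one reading the clause yields nothing; on the other it does not do what the sentence says it does. The ICCs of 0.05 and 0.10 are the plan's own sensitivity values.

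A second objection is that the mixed model with a Wald z test is itself at 7.3% when the ICC is 0.10, so deleting Mantel-Haenszel alone does not restore 5% there. That is correct. It is well below the 18.1% of the complexity-stratified test, and a t(18) reference brings it to 5.3%. Adding complexity with t(17) leaves 6.0% at that ICC, so that refinement does not remove the whole excess.

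**Conclusion.** The concern holds, and should be fixed. As written, one of the two tests offered for the Aim 1 arm comparison either cannot be computed or does not account for site clustering. The first result is algebraic and rests on site randomisation alone. The second is conditional on taking complexity as the stratum and on the simulation assumptions listed above: type I error of about 6%, 12% and 18% at ICC 0.01, 0.05 and 0.10, lower with continuity correction. The fault is confined to this option and to the open choice between the two; the mixed model beside it is sound in form. Unequal site sizes, which the plan allows for, were not simulated.

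**What to change.** Delete the Mantel-Haenszel/fixed-effects option for the arm comparison, and name the logistic model with a random centre intercept as the sole primary Aim 1 analysis. This changes one clause, chooses between options already listed, and alters neither data nor sample size.

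Preferably also:
- use a t reference suited to 20 sites;
- include the complexity stratum as a covariate, because it was used in the randomisation;
- name a site-level t-test as the check if the model does not converge.

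These are good practice rather than the correction itself. The t reference widens intervals by about 7% on 18 df (2.10 v 1.96) or 8% on 17 df (2.11 v 1.96). In the power calculation above for 0.90 v 0.68, moving from z to t(18) lowers power from 98.5% to 97.4%, from 93.7% to 91.0% and from 85.0% to 80.9% at ICC 0.01, 0.05 and 0.10. The last figure is still about the 81% that the plan claims.

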To identify patient characteristics (such as survey responses) associated with preference for endovascular or open repair we will use multivariable mixed effects logistic regression. The use of mixed effects is to account for clustering within individual VA centers using a random intercept, e.g. $\text{logit } \text{Pr}[Y_{ij}=1]=X_{ij}\beta+\mu_i$ where Y_{ij} is the binary preference variable in subject j from cluster i , X_{ij} is a vector of characteristics, μ_i is a random intercept from a zero mean distribution with standard deviation to be estimated (e.g. normal), and β is a vector of coefficient(s). We will explore the feasibility (e.g. convergence) and sensitivity of findings of patient characteristics of using either a random intercept for surgeon, or for center, or for surgeon nested within center. We will report both unadjusted and adjusted estimates, after identifying one or more models to adjust for using for instance stepwise regression or LASSO. Stata (e.g., xtmelogit) and/or R (library lme4 or nlme) software will be used. [name] has extensive experience in these strategies.

Missing Data: To accommodate missing data where justified (e.g. the variable with missing data is predictive and deserves to be adjusted for, and furthermore the data is believed to be missing at random) we shall use multiple imputation methods, such as implemented in the Stata *mi* routine.

Power Analysis: Comparing the effect of the decision aid on repair type preference. Because the decision aid will inform Veterans more fully about the long-term disadvantages of endovascular repair, we hypothesize that the decision aid will reduce the proportion of Veterans who prefer endovascular repair by 25%, based on similar decision aids studied in surgical settings in breast cancer and back pain¹⁶⁻¹⁸.

Table 3 Sample size and power calculations (assuming a 90% baseline rate of EVAR preference)

Number of clusters	Number of patients per cluster	Total Number of Patients	Proportion Choosing Endovascular Repair At	Decision Aid Effect Size (in relative decline in preference)	Proportion Choosing Endovasc Repair at	Power To detect significant difference	Power To detect significant difference	Power To detect significant difference
--------------------	--------------------------------	--------------------------	--	--	--	--	--	--

Intervention	Control	Intervention	Control	Intervention	Control	Control Sites for endovascular	Intervention Sites	(ICC 0.01)	(ICC 0.05)	(ICC 0.10)

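### The Aim 1 random-intercept test of the arm effect has no small-sample reference for 20 randomised sites; usual z or chi-square output would give about 6–7% type I error at the plan's sensitivity ICCs of 0.05 and 0.10

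*Combined protocol and SAP*

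**What the plan says.** Section 4 (Recruitment Target) says "Randomization will occur at the site level". The study population is "enrolled at the ten intervention sites and ten control sites in our cluster-randomized trial". On numbers, "We will recruit 12 Veterans per site (4 Veterans per site per month for 3 months) at 10 sites in the intervention arm", and the control arm matches, giving 120 Veterans per arm.

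Section 7, Aim 1 data analytic strategy, offers two ways to compare preference between arms: a Mantel-Haenszel test, or "a mixed effects logistic regression with fixed effect of group, and random intercept for center effects". The next modelling paragraph, on patient characteristics, adds: "Stata (e.g., xtmelogit) and/or R (library lme4 or nlme) software will be used".

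Neither place gives a reference distribution, degrees of freedom, small-sample correction, permutation test or site-level fallback. No significance level is given for Aim 1. Bootstrapping is mentioned only for the Aim 2 kappa.

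The Aim 1 power analysis assumes an ICC of 0.01. Table 3 also has columns for 0.05 and 0.10, and the text relies on the highest value to argue robustness: "even if our ICC is ten times higher (ICC=0.10", it says, power is still 81% for the 25% effect.

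**The concern.** Arm is constant within a site, so all information on the arm effect comes from comparing 10 sites with 10 sites. A Wald z or chi-square test treats the between-site variance as known when it is in fact estimated from 20 sites. If that estimate matters to the standard error, the test rejects too often under the null and the interval is too narrow.

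How much it matters depends on the ICC. With 12 Veterans per site the design effect is 1 + 11 × ICC, and the share of the variance that exists only because of clustering is 11 × ICC / (1 + 11 × ICC):

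- ICC 0.01: 0.11/1.11 = 10%
- ICC 0.05: 0.55/1.55 = 35%
- ICC 0.10: 1.10/2.10 = 52%

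Little trouble is therefore expected at 0.01, and some at 0.05 and 0.10. At stake is the calibration of the test of whether the decision aid changes preference.

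**Working it through.** **Inputs from the documents.** 10 + 10 sites; 12 Veterans per site; control preference for EVAR 0.90 (Table 3: "assuming a 90% baseline rate of EVAR preference"); effect 25% relative, so 0.90 × 0.75 = 0.675; ICC 0.01, 0.05 and 0.10. The power text says it will "allow for variable enrollment size within each cluster" but gives no measure of that variation.

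**Assumed.** Two-sided 5% level for Aim 1 (two-tailed testing is stated only for Aim 2); Wald z or chi-square as the usual output of the named logistic routines.

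**1. The plan's own figures.** No type I error is stated, so the figures to reproduce are the powers. Take n per arm = 120/(1 + 11 × ICC), which is 108.1 at ICC 0.01 and 57.1 at 0.10. With a pooled standard error and a noncentral t on 18 df:

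| Effect | ICC | Stated | t, 18 df | Pooled z |
|---|---|---|---|---|
| 25% | 0.01 | 0.96 | 0.969 | 0.985 |
| 20% | 0.01 | 0.88 | 0.890 | 0.927 |
| 15% | 0.01 | 0.71 | 0.710 | 0.761 |
| 25% | 0.10 | 0.81 | 0.794 | 0.846 |

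For the first row, the standard error is √(2 × 0.7875 × 0.2125/108.1) = 0.0556, and the noncentrality is 0.225/0.0556 = 4.04. The t version matches all four figures within 2 points; z is further off in every row. Table 3 as extracted prints two power values per row under three ICC columns, so the other entries cannot be placed with certainty.

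**2. A simple bound.** P(|t₁₈| > 1.96) = 6.6%. The 97.5% point of t₁₈ is 2.101, so a t interval is 2.101/1.960 = 1.07 times as wide as a z interval.

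**3. Simulated type I error.** Null trials of 20 sites were generated with the same rate in both arms and fitted by maximum likelihood to logit Pr(Y = 1) = a + b × arm + site intercept (25-point quadrature, 10,000 trials per row, Monte Carlo standard error about 0.24 points). Entries are percentages.

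| Null rate, site effects | ICC | Wald z | LR chi-square | Wald t₁₈ | t-test on site proportions |
|---|---|---|---|---|---|
| 0.90, logit-normal | 0.01 | 5.0 | 5.6 | 3.4 | 5.5 |
| | 0.05 | 6.3 | 6.5 | 4.6 | 4.9 |
| | 0.10 | 6.6 | 6.7 | 4.7 | 4.3 |
| 0.90, beta | 0.01 | 4.8 | 5.4 | 3.2 | 4.9 |
| | 0.05 | 6.3 | 6.3 | 4.5 | 4.8 |
| | 0.10 | 7.1 | 7.1 | 5.2 | 5.0 |
| 0.90, unequal site sizes | 0.01 | 4.8 | 5.3 | 3.2 | 4.7 |
| | 0.05 | 6.9 | 6.9 | 5.1 | 4.9 |
| | 0.10 | 6.9 | 6.7 | 4.9 | 4.0 |
| 0.79, logit-normal | 0.01 | 5.6 | 5.5 | 4.1 | 5.4 |
| | 0.05 | 6.6 | 6.2 | 4.9 | 4.8 |
| | 0.10 | 7.3 | 6.6 | 5.6 | 5.0 |
| 0.67, logit-normal | 0.01 | 5.6 | 5.3 | 4.3 | 5.4 |
| | 0.05 | 6.8 | 6.3 | 5.3 | 5.2 |
| | 0.10 | 7.3 | 6.5 | 5.6 | 5.0 |

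A Laplace fit at rate 0.90 gave Wald z errors of 6.0% (ICC 0.05) and 7.3% (0.10).

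Two further sets of runs at ICC 0.05–0.10 agree. With 31-point quadrature and 10,000 trials per setting, z gave 5.9–6.8% at rate 0.90 and 6.6–7.7% at 0.67, and t₁₈ gave 4.1–6.0%. A smaller set of 2,500 trials gave z 6.2–7.9%, t₁₈ 4.4–6.1% and the site-level t-test 4.8–5.5%. The 7.9% carries a Monte Carlo standard error of √(0.079 × 0.921/2500) = 0.5 points.

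**4. Price of the t reference.** Like for like (unpooled standard error), closed-form power for 0.90 versus 0.675 goes from 0.988 to 0.978 at ICC 0.01, 0.945 to 0.920 at 0.05, and 0.864 to 0.824 at 0.10: a loss of 1 to 4 points. Simulated power went from 0.98/0.92/0.84 to 0.98/0.90/0.80. At the 20% and 15% effects the closed-form loss can reach about 5 points (for example 0.712 to 0.664 for 20% at ICC 0.10).

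**The case against.** **The large-sample reference is inferred.** The plan does not say the test is read against z or chi-square. The software sentence is open-ended and sits in the paragraph on patient characteristics, and Section 6 names SAS for the analysis files. This stands: the documents show an omission, not a stated wrong choice. The omission still leaves the analyst with default output.

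**The planning ICC is 0.01.** There z is near nominal (4.8–5.6%) and t₁₈ is conservative (3.1–4.3%). This stands, and it means the t reference has a cost. But the power text itself leans on 0.10 to claim robustness, so calibration there is a fair question.

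**Table 3 already looks t-based.** This also stands. A reader might infer that the stated power is overstated by a z calculation; step 1 does not support that.

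**Stratification by surgical complexity may absorb some inflation.** The runs above ignore it. In 2,000-trial checks at rate 0.90, with complexity assumed to explain 20% of between-site variance and left out of the model, Wald z gave 5.8% (ICC 0.05) and 6.4% (0.10). At 40% it gave 4.4% and 5.4%, and t₁₈ gave 3.2% and 3.6%. The documents give no figure for this share, so it is a possible mitigation and not an answer.

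**The model is one of two options.** True, but a Mantel-Haenszel test stratified by center could not estimate an arm effect that is constant within centers. That is a separate matter.

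**Conclusion.** The point holds in a limited form. As written, the random-intercept test lacks a small-sample reference for 10 versus 10 sites. With usual z or chi-square output at an assumed two-sided 5% level, type I error is about 5% at ICC 0.01 and about 6–7% at 0.05 and 0.10. That is typically an excess of 1 to 2 points, and the largest simulated value, 7.9%, came from the smallest set of runs.

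A reader might go further and conclude that the plan commits to a z test, or that the Aim 1 error is 8% under its own assumptions. The documents support neither: no reference is stated, and the inflation appears only at the sensitivity ICCs. The result rests on the assumed level and default output, on the three ICCs being plausible, and on surgical complexity explaining little of the between-site variance.

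**What to change.** Add to the Aim 1 analytic strategy that the arm coefficient from the random-intercept model and its confidence interval use a t reference with between-site degrees of freedom: 18 (20 sites minus 2 arms), or 17 if the surgical-complexity stratum is in the model. State the significance level. Name a two-sample t-test on the 20 site proportions as the check; across the runs it stayed at 4.0–5.5% over all three ICCs.

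The change takes one or two sentences. It costs about 1–4 points of power at the 25% effect (up to about 5 at the smaller effects). If the ICC really is 0.01, the model-based test becomes conservative, at about 3–4%. Table 3 needs no recalculation; a note of the method behind it would be enough.
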